#### **Anakinra up-titration algorithm:**

## 6.2 Anakinra Drug Product

Anakinra is supplied in single use 1 mL prefilled glass syringes with 27 gauge needles as a sterile, clear, colorless-to-white, preservative-free solution for daily subcutaneous (SC) administration. Each 1 mL prefilled glass syringe contains: 0.67 mL (100 mg) of anakinra in a solution (pH 6.5) containing sodium citrate (1.29 mg), sodium chloride (5.48 mg), disodium EDTA (0.12 mg), and polysorbate 80 (0.70 mg) in Water for Injection, USP. Anakinra will be supplied by Sobi and dispensed through Investigational Drug Services.

## 6.3 Liso-cel treatment

Liso-cel will be infused per institutional practice and according to the Breyanzi Risk Evaluation and Mitigation Strategies (REMS).

# 7.0 POTENTIAL RISKS OF ANAKINRA TREATMENT

### Injection-site Reactions

The most common and consistently reported treatment-related adverse event associated with anakinra is injection-site reaction (ISR). In clinical trials using anakinra for treatment of Rheumatoid Arthritis 71% of patients developed an ISR, which was typically reported within the first 4 weeks of therapy. The majority of ISRs were reported as mild (72.6% mild, 24.1% moderate and 3.2% severe). The ISRs typically lasted for 14 to 28 days and were characterized by 1 or more of the following: erythema, ecchymosis, inflammation, and pain.

### Hypersensitivity Reactions

Hypersensitivity reactions including anaphylactic reactions, angioedema, urticaria, rash, and pruritus have been reported with anakinra.

If a severe hypersensitivity reaction occurs, administration of anakinra should be discontinued and appropriate therapy initiated according to institutional or clinical standard.

### Infections

In clinical trials using anakinra for treatment of Rheumatoid Arthritis, the incidence of infection was 39% in the anakinra-treated patients and 37% in placebo-treated patients during the first 6 months of blinded treatment. The incidence of serious infections was 2% in anakinra-treated patients and 1% in patients receiving placebo over 6 months. The incidence of serious infection over 1 year was 3% in anakinra-treated patients and 2% in patients receiving placebo. These infections consisted primarily of bacterial events such as cellulitis, pneumonia, and bone and joint infections. Majority of patients (73%) continued on study drug after the infection resolved. No serious opportunistic infections were reported. Patients with asthma appeared to be at higher risk of developing serious infections when treated with anakinra (8 of 177 patients, 4.5%) compared to placebo (0 of 50 patients, 0%). In open-label extension studies, the overall rate of serious infections was stable over time and comparable to that observed in controlled trials. In clinical studies and post marketing experience, cases of opportunistic infections have been observed and included fungal, mycobacterial and bacterial pathogens. Infections have been noted in all organ systems

and have been reported in patients receiving anakinra alone or in combination with immunosuppressive agents.

Antimicrobial prophylaxis and infection surveillance and treatment will be according to institutional standard for patient receiving CD19-targeted CAR-T cell therapy

### **Malignancies**

Among 5300 Rheumatoid Arthritis patients treated with anakinra in clinical trials for a mean of 15 months (approximately 6400 patient years of treatment), 8 lymphomas were observed for a rate of 0.12 cases/100 patient years. This is 3.6 fold higher than the rate of lymphomas expected in the general population, based on the National Cancer Institute's Surveillance, Epidemiology and End Results (SEER) database (SEER Incidence Crude Rates, 11 Registries, 1992-1999) An increased rate of lymphoma, up to several fold, has been reported in the Rheumatoid Arthritis population, and may be further increased in patients with more severe disease activity. Thirty-seven malignancies other than lymphoma were observed. Of these, the most common were breast, respiratory system, and digestive system. There were 3 melanomas observed in one Rheumatoid Arthritis study and its long-term open-label extension, greater than the 1 expected case. The significance of this finding is not known. While patients with Rheumatoid Arthritis, particularly those with highly active disease, may be at a higher risk (up to several fold) for the development of lymphoma, the role of IL-1 blockers in the development of malignancy is not known.

### **Hematologic Events**

In placebo-controlled studies with anakinra, 8% of patients receiving anakinra had decreases in total white blood counts of at least one WHO toxicity grade, compared with 2% of placebo patients. Nine anakinra-treated patients (0.4%) developed neutropenia (ANC < 1 x 10^9 /L). 9% of patients receiving anakinra had increases in eosinophil differential percentage of at least one WHO toxicity grade, compared with 3 % of placebo patients. 2% of patients receiving anakinra had decreases in platelet count, all WHO toxicity grade one, compared to 0% of placebo patients.

### **Immunogenicity**

As with all therapeutic proteins, there is potential for immunogenicity. In Studies using anakinra for treatment of Rheumatoid Arthritis, from which data is available for up to 36 months, 49% of patients tested positive for anti-anakinra binding antibodies at one or more time points using a biosensor assay. Of the 1615 patients with available data at Week 12 or later, 30 (2%) tested positive for neutralizing antibodies in a cell-based bioassay. Of the 13 patients with available follow-up data, 5 patients remained positive for neutralizing antibodies at the end of the studies. No correlation between antibody development and adverse events was observed. The detection of antibody formation is highly dependent on the sensitivity and specificity of the assays.

### **Hyperlipidemia**

Cholesterol elevations were observed in some patients treated with anakinra.

### **7.1 Management of Other Toxicities**

**CRS:** Patients who develop CRS will be treated according to institutional standard practice..

**ICANS:** Patients who develop ICANS will be treated according to institutional standard practice.

If a new onset CTCAE v.5 Grade  $\geq 3$  toxicity is observed, the patient will receive investigation and medical treatment appropriate for the physiological abnormalities.

## **8.0 INFORMED CONSENT OF SUBJECT AND DONOR**

Subjects will be seen at the FHCC/UWMC for consideration of treatment options for their disease. The protocol will be discussed thoroughly with the patient and other family members if appropriate, and all known and potential risks to the patient will be described. The procedure and alternative forms of therapy will be presented as objectively as possible, and the risks and hazards of the procedure explained to the patient. Consent from the patient will be obtained using forms approved by the Cancer Consortium IRB. A summary of the clinic visit detailing what was covered will be dictated for the medical record.

## **9.0 SUBJECT REGISTRATION**

Eligible subjects will be identified and registered into the system by the Clinical Coordinator's Office (CCO; Intake Office) and assigned a Unique Patient Number (UPN). The CCO will register the patient for the protocol through the Data Management Office.

Enrollment to the study will occur after data are reviewed for all inclusion and exclusion criteria by the Immunotherapy attending physician and the patient signs the study consent.

A study number will be allocated to each patient and a log of enrolled subjects will be maintained.

## **10.0 CLINICAL AND LABORATORY EVALUATIONS**

### **10.1 Screening & prelymphodepletion evaluations**

The following evaluations should be conducted within 6 weeks prior to lymphodepletion:

- 1) Medical history and physical examination including height and weight
- 2) Karnofsky performance status
- 3) Laboratory tests, including:
  - a. CBC, differential, platelet count
  - b. Renal/Hepatic Function Panel
  - c. Serum ferritin
  - d. Serum CRP
  - e. Uric acid
  - f. Quantitative serum IgG level
  - g. Prothrombin time (PT), partial thromboplastin time (PTT)
  - h. Triglycerides (non-fasting levels are acceptable)
  - i. Serum pregnancy test for females of childbearing potential within 2 weeks of planned enrollment
- 4) Baseline pulse oximetry and documentation of O2 saturation on room air

The following evaluations should be conducted within 3 months prior to lymphodepletion:

- 5) Baseline chest x-ray
- 6) Baseline 12-lead EKG

- 7) Echocardiogram or MUGA scan
- 8) Pulmonary function testing, if clinically indicated
- 9) CT/PET or CT
- 10) Bone marrow aspirate and biopsy, if clinically indicated
- 11) Lumbar puncture for CSF analysis, if clinically indicated

## **10.2 Evaluations on the day of liso-cel infusion (day 0)**

The below tests will be done as part of the clinical evaluation prior to liso-cel infusion::

1. Interval history and physical examination
2. ICE score
3. Recording of CRS and ICANS-related interventions
4. Recording of AEs
5. Blood draw for laboratory studies:
  - a. CBC, differential, and platelets
  - b. Renal/Hepatic Function Panel
  - c. Uric acid
  - d. Serum ferritin
  - e. Serum CRP
  - f. Serum IL-6 level
  - g. DIC panel without platelets (PT, PTT, fibrinogen, D-dimer)
  - h. Triglycerides (non-fasting levels are acceptable)

## **10.3 Evaluations following liso-cel infusion**

The proposed days of all assessments and laboratory evaluations are approximate and may vary due to scheduling, clinical factors, research priorities or other considerations. All timepoints may not be collected. Laboratory research evaluations may vary according to clinical and research priorities.

The following evaluations will be performed as part of the clinical evaluation after liso-cel infusion:

- 1) Interval history and physical examination approximately on day +1, +3, +7, +10, +14, +21, +28
- 2) ICE score approximately on day +1, +3, +7, +10, +14, +21, +28
- 3) Continuous recording of CRS and ICANS-related interventions through day +28
- 4) Continuous recording of AEs through day +28 as described in section XX
- 5) The following laboratory studies approximately on day +1, +3, +7, +10, +14, +21, +28:
  - a. CBC, differential, and platelet count
  - b. Renal/Hepatic Function Panel
  - c. C-reactive protein (CRP)
  - d. Serum ferritin
  - e. Serum IL-6 level
  - f. DIC panel without platelets (PT, PTT, fibrinogen, D-dimer)
  - g. Triglycerides (non-fasting levels are acceptable)
- 6) If subjects become febrile or develop symptoms of cytokine release or tumor lysis between the indicated time points, serum ferritin, CRP, DIC panel, and tumor lysis markers at additional times, may be measured as clinically indicated.

#### **10.4 Evaluations before and after each anakinra administration**

Vital signs including pulse oximetry before and 30 minutes after each anakinra administration on days 0 through day +13. For patients receiving step-up dosing, vital signs will be obtained every 4 hours per standard-of-care.

#### **10.5 Research Blood samples**

##### **Pharmacokinetic samples**

- Approximately 4 hours after the end of the first anakinra administration, up to 10mL of blood may be obtained
- Approximately 24 hours (+/- 1 hour) after the end of the first anakinra administration and immediately prior to the second anakinra administration, up to 10mL of blood may be obtained

Details regarding the tube type, handling, receiving laboratory, are detailed in a separate Research Sample Manual.

Because the clinical treatment and follow-up schedule may differ between patients, variation in the proposed blood sampling schedule is acceptable. It is also acceptable to collect fewer samples and/or less than the maximum sample number or volume depending on clinical, logistical and/or research priorities. If the patient's schedule is modified, samples may be recollected.

##### **Tissue/fluid samples**

If sampling of tissues or fluids (e.g., cerebrospinal fluid, pleural fluid, ascites, skin) is performed for clinical indications (e.g., in the context of CRS or ICANS), an additional sample may be obtained during the same procedure and sent to the FHCC for research studies. The planned procedure should be discussed with the PI.

##### **Additional research samples**

In consenting patients, other research samples may be obtained using the sample acquisition partner protocol FHCC 8682 “Collection of Samples and Data from Patients Undergoing Treatment with Commercial Chimeric Antigen Receptor Engineered T Cells”.

#### **10.6 Assessment of Disease Response to CAR-T Cell Therapy**

Objective responses to the therapeutic regimen will be assessed approximately 28 days and 90 days after liso-cel infusion using physical examination, imaging studies, and if necessary, bone marrow biopsies, as clinically indicated. If CT or PET/CT data are available, response will be defined per the Lugano criteria. The study team may contact the local oncologist office by a letter/phone call to request the results of the day 90 restaging.

#### **10.7 Long-Term Follow-up**

Subjects will be followed per institutional standard of care.

## 11.0 ADVERSE EVENT REPORTING

### 11.1 Adverse Event Definitions

- **Adverse Event**

An Adverse Event (AE) is any untoward medical occurrence in a clinical investigation subject administered a medicinal product; the event does not necessarily have a causal relationship with study drug administration or usage. An adverse event can therefore be any unfavorable and unintended sign (including an abnormal laboratory finding), symptom, or disease temporally associated with the use of a medicinal product, whether or not considered related to the medicinal product.

- **Serious Adverse Event**

A serious adverse event (SAE) is defined as an untoward medical occurrence that results in any of the following outcomes:

1. Death.
2. Life-threatening situation (i.e., with an immediate risk of death from the event as it occurred but not including an event that, had it occurred in a more serious form, might have caused death).
3. In-patient hospitalization or prolongation of existing hospitalization. Inpatient hospitalization comprises formal admission to a hospital for medical reasons, for any length of time, whether or not hospitalization extends overnight. However, hospital admissions for administration of the study drug, procedures required by the study protocol, or tumor-related diagnostic procedures are not considered serious.
4. Persistent or significant disability/incapacity or substantial disruption of the ability to conduct normal life functions.
5. Congenital anomaly/birth defect.
6. An important medical event that requires intervention to prevent one of the above outcomes.

- **Unexpected Adverse Event**

An unexpected adverse event is defined as an event that has a nature or severity, or frequency that is not consistent with the investigator brochure, protocol, or consent form.

### 11.2 Monitoring and Recording Adverse Events

Grade  $\geq 3$  AEs will be assessed by the investigator or qualified designee and recorded in the CRFs. In addition, grade 1-2 AEs contributing to the diagnosis and grading of CRS (including for example, fever, hypotension, hypoxia) and/or neurologic symptoms contributing to the diagnosis and grading of ICANS (including for example, delirium, seizure, encephalopathy) will be collected. The investigator should attempt to establish a diagnosis of the event on the basis of signs, symptoms and/or other clinical information. In such cases, the diagnosis should be documented as the adverse event and/or serious adverse event and not described as the individual signs or symptoms. The following information should be recorded:

- Description of the adverse event using concise medical terminology
- Description as to whether or not the adverse event is serious
- The start date (date of adverse event onset)
- The stop date (date of adverse event resolution or return to baseline)

- The severity (grade) of the adverse event
- A description of the potential relatedness of the adverse event to study drug or a study procedure
- Expectedness of the adverse event based on prior observed and documented adverse events
- The outcome of the adverse event

### 11.3 Grading of the Severity of an Adverse Event

AEs will be graded in severity according to the NCI Common Terminology Criteria for Adverse Events (CTCAE) Version 5.0. If a CTCAE criterion does not exist, the investigator should use the grade or adjectives: Grade 1 (mild), Grade 2 (moderate), Grade 3 (severe), Grade 4 (life-threatening), or Grade 5 (fatal) to describe the maximum intensity of the adverse event. CRS will be graded according to the 2019 ASTCT consensus criteria (Appendix A) and the 2014 NIH Lee criteria (Appendix B), the latter to allow for comparisons with historical controls. ICANS will be graded according to the 2019 ASTCT criteria (Appendix C) and the CTCAE 5.0, the latter to allow for comparisons with historical controls. In addition, therapeutic interventions related to CRS and ICANS management will be recorded.

### 11.4 Attribution of Adverse Event

Association or relatedness to the study agent will be assessed by the investigator as follows:

Definite (must have all 4)	

• Has a reasonable temporal relationship to the intervention

• Could not have readily been produced by the subject's clinical state or have been due to environmental or other interventions

• Follows a known pattern of response to intervention

• Disappears or decreases with reduction in dose or cessation of intervention and recurs with re-exposure

Probable (must have 3)	

• Has a reasonable temporal relationship to the intervention

• Could not have readily been produced by the subject's clinical state or have been due to environmental or other interventions

• Follows a known pattern of response to intervention

• Disappears or decreases with reduction in dose or cessation of intervention

Possible (must have 2)	

• Has a reasonable temporal relationship to the intervention

• Could not have readily been produced by the subject's clinical state

• Could not readily have been due to environmental or other interventions

• Follows a known pattern of response to intervention

Unlikely (must have 2)	

1. Does not have a temporal relationship to the intervention

2. Could readily have been produced by the subject's clinical state

3. Could have been due to environmental or other interventions

4. Does not follow a known pattern of response to intervention

5. Does not reappear or worsen with reintroduction of intervention

Unrelated	

• The AE is clearly NOT related to the intervention

------------------	---

For AE assessment, an AE is considered related if it is assessed as definitely, probably, or possibly related; unrelated if it is assessed as unlikely related or unrelated.

### **11.5 Adverse Event Reporting Period**

Adverse events will be monitored and recorded in study-specific case report forms (CRFs) throughout the investigative phases of the study: from the first dose of Anakinra through day 28 after the liso-cel infusion. Related AEs will be monitored until stabilization or resolution.

A subject withdrawn from the study because of an adverse event must be followed until the clinical outcome from the adverse event is determined.

The following events are *not* identified as AEs in this study:

- Disease progression or relapse.
- Medical or surgical procedures in and of themselves, including those that require hospitalization (e.g., surgery, endoscopy, biopsy procedures) are not considered AEs. However, an event or condition requiring such procedures may be an AE.

### **11.6 Adverse Event Reporting Requirements**

The investigator or designee will report events to the Fred Hutch IRB in accordance with the policies of the IRB.

## **12.0 STATISTICAL CONSIDERATIONS**

This is a pilot study to assess the efficacy of anakinra to prevent any grade CRS (primary endpoint) after liso-cel treatment in patients with B-NHL.

### **12.1 Primary endpoint:**

We will assess the efficacy of anakinra in preventing the occurrence of any grade CRS using the Bayesian optimal phase 2 (BOP2) design  with a planned interim analysis after 15 patients are treated ( $n$ , interim sample size). Unlike other existing Bayesian designs, the BOP2 design explicitly controls the type I error rate, thereby bridging the gap between Bayesian designs and frequentist designs.  $N$  denote the maximum sample size.

Based on the TRANSCEND clinical trial data in LBCL patients, the incidence of any grade CRS liso-cel therapy is estimated to be approximately 40%. Let  $p_{eff}$  denote the proportion of patients without any grade CRS (efficacy) and define the null hypothesis  $H_0: p_{eff} \leq 0.6$ , representing that the treatment is inefficacious. We assume a vague Beta(0.6,0.4) prior distribution for  $p_{eff}$ . Let  $y$  be defined as the absence of any grade CRS and the posterior probability will be computed as follows using 100,000 simulations:

$$Pr_{eff} = Pr(p_{eff} | y, n) = Beta(p_{eff} | y + 0.6, n - y + 0.4)$$

This primary endpoint will not be met if

$$Pr(p_{eff} > 0.6 | data) < \lambda \left(\frac{n}{N}\right)^\alpha,$$

where  $\lambda=0.9$  and  $\alpha=0.51$  are design parameters optimized to minimize the chance of incorrectly claiming that an efficacious treatment is not promising (i.e., type II error) under the alternative hypothesis  $H_1: p_{eff} = 0.85$ , while controlling the type I error rate (i.e., the probability of incorrectly claiming that the treatment is acceptable under  $H_0$ ) at 0.1. This design yields a statistical power of 0.928 under  $H_1$ .

## 12.2 Secondary Endpoints

- Peak CRS grade within 28 days after liso-cel infusion
- Peak ICANS grade within 28 days after liso-cel infusion
- Rate and duration of hospitalization after liso-cel treatment
- Cumulative corticosteroids dose within 28 days after liso-cel infusion
- Grade  $\geq 3$  AEs according to the NCI CTCAE Version 5.0 within the first 28 days after liso-cel administration.
- Disease response to CAR T-cell therapy approximately 28 days and 90 days after CAR T-cell infusion according to the Lugano 2014 criteria

## 12.3 Data Analysis

We will perform a first analysis when the number of enrolled patients reaches 15. The posterior probabilities of the absence of any grade CRS will be computed as described above. In our case, we will conclude that the primary endpoint is not reached if no CRS is observed in  $\leq 9$  patients in the first 15 patients treated. Since this is a pilot study, the decision to include the additional 10 patients might be considered based on both the primary and secondary endpoints.

If the total number of patients reaches the maximum sample size of 25, we will reject the null hypothesis and conclude that the primary endpoint is met if the number of patients without CRS is greater than 18 (19 or more patients with no evidence of any grade CRS); otherwise we conclude that the primary endpoint is not met.

**February 2023 update:** although our interim analysis did not meet the primary endpoint, anakinra prophylaxis was feasible, safe, and associated with low rates of mild CRS (8/15; 53%) and ICANS (3/15; 20%). Longitudinal analyses of the participants' temperature and CRP data suggested faster resolution of systemic inflammation compared to patient receiving liso-cel alone. Therefore, we will plan to treat 10 additional patients with the following protocol modification: change from SC to IV administration route, up-titration of the anakinra dose in case of breakthrough CRS or ICANS.

Statistical analysis will include descriptive statistics for which categorical variables will be summarized by number and percentage, and continuous variables will be summarized by median, standard deviation, and range. For binary endpoints, such as the proportion of patient without any grade CRS and the overall response rate (ORR), an exact 95% confidence interval using a binomial distribution will be provided. Time-to-event data will be analyzed using Kaplan-Meier method and the results will be summarized by the median with a 95% CI if appropriate.

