**Test Product, Dose, and Mode of Administration:**

In the first 15 treated patients, anakinra 200 mg/day was administered as two simultaneous 100 mg subcutaneous injections daily (approximately every 24 hours) for 14 days, with the first administration approximately 2-4 hours prior to liso-cel infusion (day 0 through day 13).

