**Prophylactic dosing:**

[figure not shown]
In the expansion cohort (n=10), anakinra will be administered first at the prophylactic dosing of 200 mg once daily intravenously (approximately every 24 hours) for 14 days, with the first administration approximately 2-4 hours prior to liso-cel infusion (day 0 through day 13).

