### **3.2 Secondary Objectives**

1. Decrease the severity of CRS by day 28 after liso-cel treatment .
2. Decrease the incidence and severity of neurotoxicity by day 28 after liso-cel treatment.
3. Decrease the rate and duration of hospitalization
4. Decrease corticosteroid usage after liso-cel treatment
5. Evaluate safety of anakinra use after CAR-T cell infusion.
6. Evaluate the effect of anakinra on liso-cel efficacy for treatment of B-NHL, as evaluated at approximately day 28 and day 90 after treatment.

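### Median, SD and range in section 12.3 can hide a change in corticosteroid use; add a count of patients given any steroid

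*Combined protocol and SAP*

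**What the plan says.** Section 3.2 sets as a secondary objective: "Decrease corticosteroid usage after liso-cel treatment". The measure given for it in section 12.2, and in the same terms in section 3.5, is "Cumulative corticosteroids dose within 28 days after liso-cel infusion". Neither list contains the proportion of patients given any steroid. Hospitalization, by contrast, is listed both as a rate and as a duration.

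Section 12.3 then gives one rule for all such variables: "continuous variables will be summarized by median, standard deviation, and range". It gives binary endpoints an exact 95% confidence interval. No mean, interquartile range or users-only summary is named for steroid dose. The documents also give no steroid-use rate, no rule for coding non-users, and no comparator or test for this endpoint.

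The data will come from two cohorts treated differently. For the subcutaneous cohort the synopsis says: "In the first 15 treated patients, anakinra 200 mg/day was administered". For the intravenous cohort it says: "In the expansion cohort (n=10), anakinra will be administered first".

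**The concern.** Cumulative steroid dose is likely to be zero for many patients and skewed among the rest. When zeros are the majority, the median is zero however many of the minority were treated and however much they received. The SD describes spread around a mean that the plan does not report, and in 10 or 15 skewed values one or two heavy users largely set it. The range depends on the single heaviest user.

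The objective is about usage, and the first question a reader will ask is how many patients needed steroids. The named summaries do not answer it. Because route and dosing changed between the cohorts, readers will set the 15 beside the 10, and the report should let them do so.

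**Working it through.** The plan states no figure for this endpoint, so there is none to reproduce.

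**Inputs.** Cohort sizes of 15 and 10 come from the synopsis. The planned statistics (median, SD, range) come from section 12.3. Two things are assumed: non-users are coded 0, and the share *q* of patients given steroids takes the values shown.

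**Step 1: when is the median 0?** With n = 15 the median is the 8th ordered value, so it is 0 if at most 7 patients are users. With n = 10 it is the average of the 5th and 6th, so it is 0 if at most 4 are users. The probability is the binomial P(X ≤ 7) or P(X ≤ 4).

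| Assumed *q* | n = 10, P(X ≤ 4) | n = 15, P(X ≤ 7) |
|---|---|---|
| 20% | 0.967 | 0.996 |
| 30% | 0.850 | 0.950 |
| 40% | 0.633 | 0.787 |
| 50% | 0.377 | 0.500 |
| 60% | 0.166 | 0.213 |

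**Step 2: chance that both medians are 0 when use is halved** from the subcutaneous (15) to the intravenous (10) cohort, taken as independent:

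- 40% to 20%: 0.787 × 0.967 = 0.76
- 50% to 25%: 0.500 × 0.922 = 0.46
- 60% to 30%: 0.213 × 0.850 = 0.18

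The result depends strongly on the starting rate.

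**Step 3: what can the documents say about the rate?** Only an indirect range. Section 12.3 reports CRS in 8 of 15 and ICANS in 3 of 15. Section 2.3.2 says that all the ICANS cases and one CRS case were grade 3 or higher. If only those severe cases received steroids, users number 3 to 4 of 15 and the median is 0. If every CRS or ICANS case did, users number 8 to 11 of 15 and the median is above 0. The width of each range reflects possible overlap between the two groups.

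**Step 4: do SD and range fill the gap?** Invented doses, n = 15, non-users 0:

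| Users' doses | Users | Median | SD | Range |
|---|---|---|---|---|
| 10, 20, 40, 80, 120, 200 | 6 | 0 | 58.7 | 0–200 |
| 10, 20, 40 | 3 | 0 | 11.3 | 0–40 |
| 10, 20, 200 | 3 | 0 | 51.4 | 0–200 |

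From the first row to the second, SD and range show the fall. From the first row to the third, users also halve, yet the median and range do not change and the SD moves only from 58.7 to 51.4.

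**Step 5: how far does one patient set the SD?** Take n = 10 with doses 0 (seven patients), 40, 120 and 600. The mean is 760/10 = 76. The squared deviations sum to 7 × 76² + 36² + 44² + 524² = 318,240, so SD = √(318,240/9) = 188.0. The heaviest user contributes 274,576/318,240 = 86% of that sum. Under the plan the entry would read median 0, SD 188, range 0–600. The quartiles are 0 and 30.

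**Step 6: what does a user count add?** In step 4 the counts are 6/15 = 40% (exact 95% CI 16.3% to 67.7%) and 3/15 = 20% (4.3% to 48.1%). The count shows the difference that the median hides. The intervals overlap widely, so it does not establish one.

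**The case against.** The strongest reply is that the plan does not rest on the median alone. It also names SD and range, and step 4 shows that both can move while the median stays at 0. A reader might infer that the stated summary cannot show a decrease at all. That goes too far: it is true of the median only, and only when both groups have under half users. If one group has more than half, a median falling to 0 is a visible decrease.

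A second reply is that use below one half is undocumented. Section 7.1 leaves CRS and ICANS to institutional practice, with no grade at which steroids start. Section 5.2 accepts pulsed steroids for disease control and does not exclude low daily doses, and the endpoint does not say whether such doses count. This stands, so the point has to be conditional.

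Third, the list in section 12.3 is not closed: "Statistical analysis will include descriptive statistics for which categorical variables will be summarized by number and percentage". Section 11.3 adds that "therapeutic interventions related to CRS and ICANS management will be recorded", so users could be counted under the present text. That is correct, but the text permits the count without committing to it.

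Fourth, replacing SD by IQR is not a cure. With 2 users of 10 the IQR is 0–0, which says less than the planned range. This also stands, and is why the range should stay and the user count should come first.

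Finally, this is a descriptive secondary endpoint in a single-arm pilot. It has no test or threshold, and steroid dose is not among the reasons section 12.3 gives for the expansion. That limits the severity.

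**Conclusion.** The point holds in a limited form and is minor. If non-users count as 0 and under half of each of two cohorts receive steroids, both medians are 0 and show no difference. SD and range may show a fall in the number of users or may miss it, and the SD belongs to a mean that is not reported. How likely this is cannot be read from the documents: the chance that both medians are 0 after a halving of use runs from 0.76 to 0.18 over the scenarios in step 2.

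Two wider inferences are not supported. A reader might conclude that the steroid median will be 0 in this trial, but the first cohort's counts allow either result (3 to 4 users, or 8 to 11, of 15). A reader might also extend the point to hospitalization, but its rate is already listed beside its duration, so the question of how many is covered there.

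**What to change.** In section 12.3, for corticosteroids:

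- Report first the number and percentage of patients with any use within 28 days, with the exact 95% CI already planned for binary endpoints, separately for the subcutaneous (n = 15) and intravenous (n = 10) cohorts.
- State that non-users count as a dose of 0, and whether steroids given for reasons other than CRS or ICANS count.
- Then report dose by median, IQR and range in all patients and, descriptively, among users, who may be only a few.

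For other continuous variables, report median with IQR and range, and give an SD only with a mean. Keep the range throughout. Hospitalization needs no separate change.

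The cost is a few sentences. The cumulative dose already requires each patient's steroid record, so no new data are needed. The change makes the result interpretable; it does not make a comparison of 15 with 10 patients any more precise.
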